10. DATA ANALYSIS

1. Data Quality Assurance

The PI will be solely responsible for the accuracy of the data. Single data entry will be performed with plans to check 10% of primary variables as a quality control. Single data entry error rates are slightly higher than 0.5% when performed by trained staff and the minimally improved error rate through double data entry is outweighed by substantial cost savings for single data entry.²⁵ Data anomalies will be reviewed by the PI and clarification and/or correction will be performed. Incomplete entries will be reviewed and corrected if information is available.

2. Data Entry and Storage

Data will be entered on a UTH google drive spreadsheet file, with permission to access controlled by the PI. Data collected by the RA from the voiding diary and survey outcome measures will be entered into the spreadsheet. Data will be coded by subject ID.

The RA will have the linking log of the patients to their subject ID in her password-protected desktop in the TIRR Memorial Hermann Research building.

5 years after manuscript publication, the paper reports will be placed into the shredder bins for destruction.

11. SAMPLE SIZE AND STATISTICAL METHODS

1. Determination of Sample Size

Sample size will be determined from **Aim 1.1**. Assuming that 40% of the subjects in the control group are able to reduce their bladder medications (placebo effect), the study would require a sample size of 21 for each group (i.e. a total sample size of 42), to achieve a power of 80% for detecting a difference in proportions of 43% between the two groups (83% in TTNS group –40% in control group) at a two sided p-value of 0.05. Accounting for 40% dropout, we will recruit 30 subjects in each arm for a total of 60 subjects. In **Aim 1.2**, the NBSS has demonstrated responsiveness to change after bladder chemodenervation with a mean difference of 11.8 (11),²² which would require a sample size of 20. For **Aim 2.1**, a 7±17 point improvement in the I-QOL score was observed after 4 weeks of TTNS use in our pilot study. We expect the control group to have minimal improvement in I-QOL scores due to placebo effect, estimated as 3 points. With power of 80% and a more conservative standard deviation of 4 points, we need a sample size of 22 in total by two-sample two-sided t-test at a type I error rate of 0.05. The sample size determined by Aim 1.1 is sufficient for this aim.

2. Statistical and Analytical Plans

Patients will be randomized to control and TTNS at a 1:1 ratio by computer-generated sequences, with stratified allocation in blocks of 4 controlling for complete SCI, with the investigator blinded to the treatment allocation. Changes in outcomes listed in Aim 1 and 2 will be compared between groups by two-sample two-sided t-test or Wilcoxon rank-sum test. Descriptive statistics and mean plots will be provided for the longitudinal measurements. Multilevel mixed-effects regression models will be used for longitudinal analyses of treatment effects, controlling for confounding variables including age, sex, severity of SCI, compliance (number of sessions), and OAB medication dosages. Multiple testing will be adjusted by Bonferroni correction if necessary. Non-random missing data will be analyzed using the method in Ibrahim and Molenberghs.²³ Considering the unknown long-term effects of TTNS, we may not see significant treatment effect on some outcomes by conventional (frequentist) analyses. We plan a Bayesian analysis (with either skeptical or neutral priors) to estimate the probability (with 95% credible intervals) of treatment effect. Conventional analysis will be performed in SAS 9.4 (SAS Institute, Cary NC) and Bayesian analysis will be performed in R 3.5.0 using packages like R2WinBUGS.

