3. STUDY POPULATION

1. List the number of subjects to be enrolled.

60 subjects. Consecutive SCI clinic encounters meeting the inclusion/exclusion criteria will be asked to enroll. Children and pregnant women will be excluded.

2. Criteria for Recruitment

- Initial screening will be performed in the clinic with the subject and PI
- In those interested, they will be given an IRB-approved consent form to review and to sign.
- Those with tetraplegia will unlikely have the ability to sign and we will have a 3rd party attest to the consent.
- Patients will ideally decide to participate in clinic, but can always decide at a later date and return to clinic to trial the TTNS as part of the I/E criteria.
- Flyers will be posted and distributed in the outpatient clinic to increase study awareness.

3. Inclusion Criteria (table 1)

Inclusion criteria: 1) ages 18-75 years; 2) SCI performing IC; 3) up to 2 anticholinergic OAB medications; 4) stable OAB medications in the past 2 months; 5) SCI neurologic level above T10; 6) English and Spanish speaking. Subjects that satisfy initial screening and willing to participate in the trial will have electric stimulation placed to attempt toe flexion as a check of the tibial nerve integrity. Those who cannot achieve toe flexion will be excluded.

Table 2. Inclusion and Exclusion Criteria

Inclusion Criteria	Exclusion Criteria
18-75 years old Traumatic and Non-traumatic SCI performing IC	Past history of genitourinary diagnoses or surgeries History of CNS disorders and/or peripheral neuropathy
Up to 2 anticholinergic OAB medications	Pregnancy
No changes in OAB medications	Lower motor neuron bladder
Neurologic level of injury above T10	Concern for tibial nerve pathway injury
English and Spanish speaking	Absence of toe flexion or AD with electric stimulation Bladder chemodenervation in past 6 months Potential for progressive SCI including neurodegenerative SCI, ALS, cancer myelopathy, Multiple sclerosis, transverse myelitis

SCI= spinal cord injury; IC= intermittent catheterization; OAB= overactive bladder; T10= thoracic level 10; CNS= central nervous system; AD= autonomic dysreflexia

4. Exclusion Criteria (table 1)

Subjects meeting any of the exclusion criteria at baseline will be excluded from participation:

- History of genitourinary diagnoses (i.e. prostate hypertrophy, overactive bladder, cancer, etc.)

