- Potential for progressive SCI including neurodegenerative SCI, ALS, cancer myelopathy, Multiple sclerosis, transverse myelitis
- History of central nervous system disorder (i.e. prior SCI, stroke, brain injury, Parkinson's disease, MS, etc.)
- History of peripheral neuropathy
- pre-SCI symptoms of peripheral neuropathy (numbness and/or tingling in feet, sharp/jabbing/burning pain in feet, sensitivity to touch, lack of coordination, muscle weakness, etc.)
- Pregnancy
- Known injury to the lumbosacral spinal cord or plexus, or pelvis with associated neuropathy
- concern for tibial nerve pathway injury
- absence of toe flexion or autonomic dysreflexia during electric stimulation test
- bladder chemodenervation in prior 6 months

5. Withdrawal Criteria

Possible reasons for discontinuation of study intervention:

- Intolerable incontinence after discontinuation of bladder medications
- Intolerant to electric stimulation
- Non-compliance

To mitigate non-compliance, a stipend for effort in completing voiding diary will be provided at \$10 per day (2 days per month). An additional \$20 will be provided for logging bladder medication use and TTNS use/settings monthly. If both voiding diary and TTNS diary are reported, a \$10 bonus will be provided, therefore \$70 month 1, and \$50 for each months 2 and 3. At most per subject= \$170 for the 3-month trial per subject. Subjects will also receive reimbursement for travel for the urodynamic studies up to \$200 per trip (two urodynamic studies = up to \$400 per subject) and if medication reduction requires new prescriptions to cover co-payments when applicable up to \$50 total per subject.

6. Subject Replacement

Subjects who drop out will be replaced by recruitment from the SCI clinic and asking for informed consent from those who meet the I/E criteria.

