5. STUDY DESIGN

Anticipated number of patients to screen: 80

- Anticipated number of patients to enroll: 60
- Anticipated drop out or loss to follow-up: 6

Approximate time to complete study recruitment: 1 year

Expected duration of subject participation: 3-months. 3-months was selected as a fair assessment of efficacy. Clinically, medications are determined efficacious based on 1-month or less of use.

TTNS protocol: Same TTNS setting will be used as protocols HSC-MS-15-0806 and HSC-MS-17-0423. Electrodes 2 inch by 2 inch will be placed according to anatomic landmarks, with the negative electrode behind the internal malleolus and the positive electrode 10cm superior to the negative electrode, verified with rhythmic flexion of the toes secondary to stimulation of the flexor digitorum and hallucus brevis. The intensity level will be set to the amperage immediately under the threshold for motor contraction. If there is not contraction seen, patients will be excluded. In addition, if the patient perceives pain, the intensity will be lowered until comfortable. Stimulation frequency of 10 Hz and pulse width of 200ms in continuous mode will be used.^{13, 14}

Sham protocol and rationale: Toe flexion will be attempted, as in the TTNS protocol. Then the stimulation will be reduced to 1 mA for 30 minutes. Rationale: In order to make this a convincing blind, the TTNS protocol must be simulated closely as subjects may interact and discuss. Rather than turning the device off, they will be instructed that the stimulation required is below motor threshold, at 1 mA. Based on the knowledge of the pilot trial requiring about 40mA for TTNS, and the amperage for needle-driven PTNS adjacent to the tibial nerve at 0.5 – 1mA, it is unrealistic that 1mA via surface electrodes is sufficient to activate the tibial nerve. Both TTNS and sham participants will be instructed to use the device for 30 minutes, 5 days per week.

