Subjects will have their first study visit after their normal clinic visit. Once consented, we will trial TTNS for a response of toe flexion. If they have a response, they will be included in the study. If no response or not tolerating electric stimulation, they will not be included in the study.

Participants will have direction in clinic on the use of the Stamobil+, including written, oral, and smartphone images/video if they have access.

The electric stimulation protocol will use stimulation frequency of 10 Hz and pulse width of 200ms in continuous mode for 30 minutes daily, beginning as soon as possible. The goal is 5 days per week of TTNS use for 3-months.

Subjects will be called weekly to capture the information of the TTNS log and to monitor progress of protocol. They will also be reminded to change electrodes weekly. 3 days prior to the NBSS call, the RA will contact the subjects to remind them to begin recording in their voiding diary for 2 days.

- *Final Study Visit:*

Upon completion of the 3-month study period, final voiding diary information will be collected and the post-trial questionnaires will be conducted.

- *Post Study Follow up and Procedures*

The data will be statistically analysed in the post-study follow up. Subject participation is not required.

- *Discontinuation Visit and Procedures*

If withdrawal occurs, no evaluation will be required for the final study visit, regardless of the withdrawal reason. There are no safety risks in withdrawing from this study at any point. OAB medications can be resumed at the prior efficacious dose.

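### Section 11.1 says 60 recruits allow for 40% dropout from a required 42, but without additional replacements 60 covers at most 30% (18 losses)

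*Combined protocol and SAP*

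**What the plan says.** Section 11.1 (Determination of Sample Size) sizes the trial on Aim 1.1, the proportion of subjects able to reduce their bladder medication. For the contrast "83% in TTNS group –40% in control group", with 80% power and a two-sided level of 0.05, it states that "the study would require a sample size of 21 for each group (i.e. a total sample size of 42"). The next sentence moves from the requirement to the intake: "Accounting for 40% dropout, we will recruit 30 subjects in each arm for a total of 60 subjects".

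Sections 3.1 and 5 give the same intake: "60 subjects. Consecutive SCI clinic encounters meeting the inclusion/exclusion criteria will be asked to enroll" and "Anticipated number of patients to enroll: 60". Section 5 adds a loss figure of its own: "Anticipated drop out or loss to follow-up: 6".

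Two other places bear on losses. Section 3.6 (Subject Replacement) says "Subjects who drop out will be replaced by recruitment from the SCI clinic", with no number and no statement on whether replacements fall within the 60. Section 6.4, on the discontinuation visit, says "If withdrawal occurs, no evaluation will be required for the final study visit, regardless of the withdrawal reason".

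**The concern.** A dropout allowance is normally read as the share of those recruited who may be lost while the required number still remains. On that reading, section 11.1 tells an IRB or a monitor that the trial keeps its 42 subjects after losing 24 of 60. It does not: it keeps 42 only up to 18 losses.

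This sentence is the stated justification for N = 60, so the plan claims a robustness that 60 recruits do not give by themselves. Losses matter because no final evaluation is required after withdrawal, so a subject who leaves early may have no week-12 assessment. What is at stake is a stated property of the design. The choice of 60 is not itself in question.

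**Working it through.** **Inputs.** Required: 21 per arm, 42 in all. Recruited: 30 per arm, 60 in all. Allowance: 40%. Response rates: 0.83 and 0.40. Two-sided level 0.05, power 80% (all section 11.1). Anticipated losses: 6 (section 5). Allocation 1:1 (section 6.2).

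**1. The plan's base figure.** Section 11.1 names no formula. The pooled normal formula, with p̄ = (0.83 + 0.40)/2 = 0.615, gives

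n = [1.960·√(2·0.615·0.385) + 0.842·√(0.83·0.17 + 0.40·0.60)]² / 0.43² = 18.9, so 19 per arm.

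With continuity correction the result is 24 per arm. The stated 21 lies between these and within 2 of the pooled result. I take it as the plan's own requirement.

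**2. The dropout step.**
- Remaining after 40% loss: 60 × (1 − 0.40) = 36, or 18 per arm. Shortfall: 42 − 36 = 6.
- Largest loss that leaves 42: (60 − 42)/60 = 18/60 = 30%, or 9 per arm.
- Recruits needed for 42 to remain after 40% loss: 42/(1 − 0.40) = 70, or 35 per arm.

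The stated 60 is therefore not reproduced by dividing by 0.60. It is reproduced by multiplying: 21 × 1.4 = 29.4, rounded up to 30 per arm. It also fits 40% written where 30% was meant, since 42/0.70 = 60. The documents do not show which happened.

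**3. Replacement.** If replacements are added to the 60, ten more subjects (70 in all) give 70 × 0.60 = 42. The cover then comes from section 3.6 and not from the inflation in section 11.1.

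**4. The loss anticipated in section 5.** 6/60 = 10%, and 60 − 6 = 54 remain, 27 per arm.

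**5. Power at these sizes.** Completers only, equal loss per arm, 0.83 against 0.40, two-sided 0.05. Normal-approximation power is Φ{[0.43 − c − 1.960·√(2·0.615·0.385/n)] / √(0.3811/n)}, where 0.3811 = 0.83·0.17 + 0.40·0.60, with c = 0 (pooled) or c = 1/n (continuity-corrected). The other two rows sum the binomial probabilities of all outcomes that the test rejects.

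| Method | 18 per arm | 21 per arm | 27 per arm |
|---|---|---|---|
| Pooled normal | 78% | 84% | 92% |
| Continuity-corrected normal | 65% | 74% | 87% |
| Uncorrected chi-square, exact enumeration | 81% | 85% | 92% |
| Fisher's exact test | 69% | 74% | 88% |

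Going from 21 to 18 per arm costs about 4 to 9 points, depending on the method. At 27 per arm every method is above 80%.

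**The case against.** The strongest reply is that nothing practical follows. Section 5 anticipates 6 losses, and 54 completers are well above 42. Even at 40% loss, the uncorrected chi-square test still gives about 81% power, so by that test only the headcount is missed. This stands as a limit on the impact. It does not make the sentence true, because 42 is the plan's own requirement and the shortfall of 6 does not depend on any test.

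A second reply is that dropouts will be replaced, which on an ordinary reading protects the number of completers. This also softens the point. But no section gives a total above 60 or ties replacement to the 40%, and sections 3.1, 5 and 11.1 all use 60.

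A third is that subjects who withdraw may still contribute data: diary data are collected weekly by telephone, and section 11.2 plans mixed models and methods for missing data. The completers-only power figures may therefore be somewhat pessimistic. Section 11.1 nevertheless sizes the trial on a simple proportion in 42 subjects.

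A reader might infer three stronger things that the documents do not support:
- *The trial is underpowered, or 60 is too few.* At the anticipated losses it is not. At 40% loss the answer depends on a test that section 11.1 does not name.
- *The 10% in section 5 and the 40% in section 11.1 contradict each other.* An expected loss can stand beside a larger safety allowance. The fault is only that neither figure is labelled.
- *The sponsor multiplied by 1.4 in error.* The arithmetic fits, but a slip of 40% for 30% fits too.

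**Conclusion.** The point holds as a correction to a stated property of the design. Without replacements beyond 60, section 11.1 overstates the tolerated dropout: 60 recruits leave the required 42 up to 30% loss, and at 40% loss they leave 36. This rests only on the plan's own 42, 60 and 40%, and on reading dropout as a share of those recruited.

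The consequence is modest. N = 60 is ample under the anticipated 6 losses. The power figures are illustrative: they assume completers only, equal loss in the two arms, and a method that the plan leaves open. No single power value at 36 should be set beside the plan's 21 per arm for 80%. The pooled normal formula, for example, gives 84% at 21, so quoting its 78% at 18 next to the plan's 80% would understate the loss. The correction is worth making because it concerns the sentence that justifies the sample size, and it needs only wording.

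**What to change.** Keep N = 60 and restate section 11.1 by headcount, for example: *60 recruited leaves 42 (21 per arm) if dropout is at most 30% in each arm; at 40% dropout without additional replacements 36 remain.* The condition in each arm matters, because 18 losses spread unevenly would leave one arm below 21.

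In section 5, label the 6 losses (10%) as the expected loss, and refer to 30% as the allowance. In section 3.6, say whether replacements count within the 60 or are added to it.

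If the sponsor does intend a 40% allowance, the text must say that replacement on top of the 60, to 70 enrolled in all, supplies it. Sections 3.1 and 5 would then need the same total.

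If power at 36 is to be quoted, use the method that gave 21 per arm, and name it.

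The cost of the main correction is wording, plus a less favourable stated tolerance: 30% in place of 40%. The alternative costs up to 10 further enrolments.

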Medication reduction protocol: Subjects will be using up to 2 anticholinergic OAB medications. Subjects generally use similar medications with a common approach- maximize one medication before adding a second medication. The PI will provide a weekly weaning schedule, individualized for each subject. No changes will occur during the first 2 weeks of TTNS. Starting week 3, the secondary OAB medication will be halved if possible, otherwise discontinued. Should the subject tolerate this, weaning will continue until one medication is discontinued, then the other. If the subject does not tolerate weaning, they will remain on the lowest, tolerable dose and we will attempt weaning the following week.

- Information gathered:
 - Clinical demographics, morbidity, and Neurologic Exam findings from interview with subjects, exam, and EMR review.
 - Bladder diary will include:
 - use of TTNS with amperage and presence of toe flexion, and pain score 0-10
 - log of catheterization, volumes
 - log of incontinence episodes
 - Description of other observed changes, including but not limited to: fatigue, vision changes, mental status, bowel program changes, and sexual function changes.
 - I-QOL at baseline initial visit and then at 3-month follow-up. Can be conducted over phone.

- NBSS at baseline and every 4 weeks (monthly) and at the 3-month follow-up. Can be conducted over phone.
- Anticholinergic survey at baseline and then at 3-month follow-up. Can be conducted over phone.
- TTNS satisfaction survey at 3-month follow-up. Can be conducted over the phone.
- Information will be tabulated on an Excel spreadsheet on my personal work desktop, password protected. Any paper data (bladder diary) will be de-identified and retained in a locked drawer in the locked office of the PI.
- General self-efficacy at baseline, week 6 and at the end of the trial. Can be conducted over the phone.
- CD-RISC at baseline, week 6 and at the end of the trial. Can be conducted over the phone.
- The medication and TTNS adherence survey at baseline then every 4 weeks. Can be conducted over the phone.
- The medication and TTNS % survey at baseline then every 4 weeks. Can be conducted over the phone.

1. Summary of Study Design

A randomized control trial of TTNS v sham-control in chronic SCI (n=60) performing intermittent catheterization on OAB medications will be performed to address the following Specific Aims:

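### Section 11.1 sizes the I-QOL aim on an unsourced SD of 4 when the pilot gives 17; the total of 22 does not follow from its inputs, and the adequacy claim is unsupported.

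*Combined protocol and SAP*

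**What the plan says.** Section 11.1 takes the trial's size from Aim 1.1: 21 per group, 42 in total. It then adds: "Accounting for 40% dropout, we will recruit 30 subjects in each arm for a total of 60 subjects". For Aim 2.1 it reports that "a 7±17 point improvement in the I-QOL score was observed after 4 weeks of TTNS use in our pilot study", assumes a 3-point placebo improvement in controls, and continues: "With power of 80% and a more conservative standard deviation of 4 points, we need a sample size of 22 in total". The test is a two-sided two-sample t-test at 0.05. The paragraph ends: "The sample size determined by Aim 1.1 is sufficient for this aim".

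Section 2 lists a higher I-QOL score with TTNS than in controls as Secondary Objective 1. Section 5 schedules the measurement as "I-QOL at baseline initial visit and then at 3-month follow-up", and expects fewer losses than section 11.1 does: "Anticipated drop out or loss to follow-up: 6".

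**The concern.** Required sample size rises with the square of the SD, so a planning SD smaller than the observed one lowers the requirement. Calling 4 conservative next to 17 reverses the meaning of the word. The total of 22 also looks too small for a standardised difference of 1.0.

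What is at stake is how the I-QOL result will be read. The plan tells readers that the trial is large enough for its first secondary objective. If it is not, a non-significant result could be taken as evidence that home TTNS does not improve quality of life, when the trial had little chance of showing a difference of the size expected.

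**Working it through.** **Inputs, all from section 11 unless noted.** Improvement of 7 points with TTNS and 3 with control, so the difference is 7 − 3 = 4 (the plan does not state the difference itself). SD 4 as planned, and ±17 from the pilot. Two-sided α = 0.05, 80% power, 1:1 allocation, two-sample t-test.

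Evaluable totals considered:
- 36 = 60 × (1 − 0.40), the 40% dropout of section 11.1
- 42, the Aim 1.1 requirement
- 54 = 60 − 6, the losses expected in section 5
- 60, no losses

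**Step 1: the plan's figure of 22.** The normal approximation is n per arm = 2(1.96 + 0.8416)² × (SD/difference)² = 15.70 × (4/4)² = 15.7, which rounds up to 16 per arm, 32 in total. The exact noncentral-t calculation gives 16.7, so 17 per arm, **34 in total**. With 22 (11 per arm), power is 60.7% (exact) or 65.0% (normal).

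Other readings do not give 22 from the stated inputs:
- one-sided test: 26 (normal) or 28 (exact)
- difference of 7 with SD 4: 12 or 14
- one-sample or paired test at a standardised difference of 1: 10
- Wilcoxon test, efficiency 0.955: 36

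A total of 22 needs an unstated value: an SD of about 3.2, or a difference of 5 with SD 4 (15.70 × (4/5)² = 10.05, so 11 per arm; exact power 79.6%).

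**Step 2: direction of the SD change.** (17/4)² = 18.1. At SD 17 the normal approximation gives 15.70 × 18.06 = 283.5, so 284 per arm. The exact calculation gives 285 per arm, **570 in total**, before dropout.

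**Step 3: is the Aim 1.1 size sufficient?** Exact power for a 4-point difference:

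| SD | 36 evaluable | 42 | 54 | 60 | Total for 80% power |
|---|---|---|---|---|---|
| 4 | 83% | 89% | 95% | 97% | 34 |
| 6 | 49% | 56% | 67% | 72% | 74 |
| 8 | 31% | 35% | 44% | 48% | 128 |
| 10 | 21% | 24% | 30% | 33% | 200 |
| 17 | 10.5% | 11.5% | 13.6% | 14.6% | 570 |

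The standardised difference d detectable with 80% power fixes two limits: 4/d is the largest SD at which the claim holds, and 17d is the detectable difference at SD 17. The expected 95% CI half-width at SD 17 is t(0.975, 2n − 2) × 17 × √(2/n), with n per arm.

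| Evaluable | d | Largest SD (4/d) | Detectable at SD 17 | CI half-width at SD 17 |
|---|---|---|---|---|
| 36 | 0.961 | 4.2 | 16.3 | 11.5 |
| 42 | 0.886 | 4.5 | 15.1 | 10.6 |
| 54 | 0.777 | 5.1 | 13.2 | 9.3 |
| 60 | 0.736 | 5.4 | 12.5 | 8.8 |

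**The case against.** Five points can be made for the plan.

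- **I-QOL is secondary and does not set the sample size.** This is true and limits the severity. The plan nevertheless chose to make a positive adequacy claim for it.
- **The error in the 22 does no harm.** This stands: 34 is below both 42 and 36, so sufficiency would survive if the SD really were 4. The failure lies in the SD.
- **The ±17 is a weak planning figure.** It is unlabelled, was observed at 4 weeks whereas this trial measures I-QOL at 3 months, and comes from a small pilot; the home pilot in section 1 was single-arm with 16 subjects. These cautions stand, but they do not rescue SD 4. If ±17 were a standard error, the SD would be larger still. If all 16 subjects contributed and the changes were normal, a 95% interval for the SD is about 12.6 to 26.3. The claim already fails at SD 6.
- **The 22 may come from a misstated placebo estimate.** A difference of 5 would give it by normal approximation. This is possible, so the inputs and the total need to be reconciled by the sponsor.
- **Section 11.2 already warns of non-significance.** It says "we may not see significant treatment effect on some outcomes by conventional (frequentist) analyses" and plans a Bayesian analysis. That softens the consequence. But it attributes the risk to unknown long-term effects of TTNS and does not withdraw the adequacy claim in section 11.1.

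**Conclusion.** The concern holds. The SD of 4 is unsourced and anti-conservative relative to the only I-QOL spread reported. The total of 22 should be 34 on the inputs as written. The sufficiency statement is unsupported, and false at SD 17: a true 4-point difference would be missed about 85 to 90% of the time, depending on whether 60 or 36 subjects are evaluable.

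This rests on reading ±17 as the SD of change, on carrying a 4-week value to 3 months, and on a between-group difference of 4. The finding that sufficiency is unsupported does not need 17 to be exact, because any SD above about 5.4 defeats the claim even with no losses. The Aim 1.1 basis for the sample size is not affected. This should be corrected, but it does not call the trial's size for Aim 1.1 into question.

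**What to change.** In section 11.1, remove the description of SD 4 as conservative and delete the sentence "The sample size determined by Aim 1.1 is sufficient for this aim". Replace them with text such as:

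> *The pilot I-QOL change had a spread of ±17 at 4 weeks, taken here as an SD. At that SD, power for a 4-point difference is about 11% with 36 evaluable subjects, 12% with 42, 14% with 54 and 15% with 60. The difference detectable with 80% power is about 16.3, 15.1, 13.2 and 12.5 points respectively. I-QOL is a secondary outcome, will be reported with a 95% confidence interval, and the trial is not powered for it.*

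The sponsor should confirm what ±17 represents. If SD 4 is kept, justify it from data, state the between-group difference, and reconcile it with the total: 34 for a difference of 4.

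The cost is wording in one section and a less favourable statement of power for a secondary aim. No extra patients and no change of design are needed.

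### NBSS, I-QOL and side-effect changes are to be tested without baseline adjustment, and the mixed model does not say how baseline enters; the test is valid but gives up precision

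*Combined protocol and SAP*

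**What the plan says.** The combined protocol and SAP, section 11.2 (Statistical and Analytical Plans), gives one between-group rule for these outcomes: "Changes in outcomes listed in Aim 1 and 2 will be compared between groups by two-sample two-sided t-test or Wilcoxon rank-sum test". No covariate is attached to it, and no section mentions analysis of covariance.

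The same section adds a second analysis: "Multilevel mixed-effects regression models will be used for longitudinal analyses of treatment effects". The covariates it lists for that model are given only by example: "controlling for confounding variables including age, sex, severity of SCI, compliance (number of sessions), and OAB medication dosages". The outcome's own baseline value is not named, and the plan does not say which of the two analyses is the main one.

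Section 5 (Study Design, information gathered) shows that the baselines exist:

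- NBSS: "NBSS at baseline and every 4 weeks (monthly) and at the 3-month follow-up". The schedule of events places the later assessments at weeks 4, 8 and 12.
- I-QOL: "I-QOL at baseline initial visit and then at 3-month follow-up".
- Side effects: "Anticholinergic survey at baseline and then at 3-month follow-up".

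Section 6 (Randomization and Blinding) stratifies allocation by complete or incomplete SCI. NBSS belongs to Primary Objective 2. I-QOL and anticholinergic side effects are Secondary Objectives 1 and 2.

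**The concern.** Testing raw change fixes the weight on the baseline value at 1. Estimating that weight from the data, as ANCOVA does, is in large samples never less precise in a randomised trial. The plan pays for the baseline measurements but uses them in the less efficient way, and it leaves the stratification factor out of the test.

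There is a second consequence. Suppose the arms differ at baseline by a chance amount d. With equal SDs, a difference of ρd is expected at follow-up, but the change score subtracts all of d. The observed treatment difference is then shifted by (1−ρ)d in the opposite direction. Stratifying on completeness of injury does not ensure balance on NBSS or I-QOL.

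The mixed model does not clearly repair this. If baseline is a response row with arm means left free, the arm-by-time contrast roughly reproduces the change score. If baseline is a covariate, or a response with one common mean for both arms, the precision is recovered. The plan does not choose. I-QOL and the side-effect survey have one post-baseline value each, so later visits cannot supply the missing precision.

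**Working it through.** **Inputs from section 11.1 (Determination of Sample Size).** NBSS: 11.8 (11), read here as mean and SD of change. I-QOL: "7±17 point improvement in the I-QOL score was observed after 4 weeks of TTNS use in our pilot study", against "minimal improvement in I-QOL scores due to placebo effect, estimated as 3 points", so the difference is 7 − 3 = 4; the planning SD is 4.

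**Numbers per arm.** 21 is the planned evaluable number. 27 follows from section 5's six expected losses, (60 − 6)/2. 18 follows from section 11.1's 40% dropout, 30 × 0.6. 30 is full enrolment.

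**Assumed.** ρ of 0.3 to 0.9 and equal SD σ at both times. Neither is in the documents.

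**The plan's own figures first.** I-QOL is the only sample size that section 11.1 ties to a named two-sample t-test. Difference 4, SD 4, 80% power and two-sided 0.05 need 17 per arm (34 in total) by noncentral t. The stated 22 in total gives 60.7% power, so that figure does not reproduce. For NBSS, 11.8/11 needs 15 per arm at 80% power and 20 per arm at 90%, so the stated 20 matches only as a per-arm number at 90%. These are separate matters; the comparison below uses the stated effects and SDs.

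**Variance.**

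- Change score: 2σ²(1−ρ)
- ANCOVA: σ²(1−ρ²)
- Ratio: (1−ρ²)/[2(1−ρ)] = (1+ρ)/2, which is 0.65, 0.75, 0.85 and 0.95 at ρ = 0.3, 0.5, 0.7 and 0.9

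**Power (%).** Noncentral t with n per arm. Change score: SD as stated, 2n−2 df. ANCOVA: SD × √[(1+ρ)/2], 2n−3 df.

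| Outcome, effect, SD | n per arm | Change score | ρ 0.3 | ρ 0.5 | ρ 0.7 | ρ 0.9 |
|---|---|---|---|---|---|---|
| NBSS, 11.8, 11 | 18 | 87.8 | 97.2 | 95.0 | 92.3 | 89.3 |
| NBSS, 11.8, 11 | 21 | 92.4 | 98.8 | 97.5 | 95.7 | 93.5 |
| NBSS, 11.8, 11 | 27 | 97.2 | 99.8 | 99.4 | 98.7 | 97.8 |
| NBSS, 8 (assumed), 11 | 21 | 63.3 | 81.3 | 75.6 | 70.3 | 65.5 |
| NBSS, 8 (assumed), 11 | 27 | 74.6 | 90.2 | 85.7 | 81.2 | 76.7 |
| I-QOL, 4, 4 | 30 | 96.8 | 99.7 | 99.3 | 98.5 | 97.4 |
| I-QOL, 4, 17 | 30 | 14.6 | 19.9 | 17.9 | 16.3 | 15.1 |

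The 8-point effect is an illustration, not a figure from the plan. A value below 11.8 is worth examining because 11.8 is a response to chemodenervation, and section 11.1 expects some placebo response in controls on medication and I-QOL.

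**Over-correction.** Take a one-standard-error baseline imbalance in NBSS at 27 per arm. With SD of change 11, σ = 11/√[2(1−ρ)], d = σ√(2/27), and the shift is (1−ρ)d.

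| ρ | σ | d | Shift (points) |
|---|---|---|---|
| 0.3 | 9.3 | 2.5 | 1.8 |
| 0.5 | 11.0 | 3.0 | 1.5 |
| 0.7 | 14.2 | 3.9 | 1.2 |
| 0.9 | 24.6 | 6.7 | 0.7 |

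The standard error of the change-score difference is 11 × √(2/27) = 2.99, so these shifts are 0.59, 0.50, 0.39 and 0.22 standard errors.

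**Small-sample cost.** Estimating the slope inflates the ANCOVA variance by about 1 + 1/(2n−4). At 21 per arm this is 1 + 1/38 = 1.026. At ρ = 0.9 the ratio becomes 0.95 × 1.026 = 0.975, still below 1. The power table does not include this factor, so its gains are slightly generous.

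**The case against.** The best defence is that nothing here is invalid. Over randomisation the change-score comparison is unbiased and keeps its type I error. That stands: this is a point about efficiency. A reader might infer that chance baseline imbalance is simply left in the result. It is not; the change score subtracts the imbalance, and what remains is the over-correction of (1−ρ)d.

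A reader might also infer that the mixed model leaves out the outcome's baseline. The text does not establish this. The covariate list is introduced as examples, and a longitudinal model may carry baseline as a response. For NBSS, with three post-baseline visits, a common baseline mean would recover about the ANCOVA precision. All that can be said is that the plan does not specify it.

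The gain is also modest on the plan's own figures. At 11.8 points NBSS power is already 92–97% at 21–27 per arm. For I-QOL it is about 97% at 30 per arm with SD 4. With the pilot SD of 17, adjustment leaves power at 15–20%; the difficulty there is the SD assumption, which this change does not solve. These limits stand and keep the point below a critical one. They do not remove it: the adjustment needs no new data, and it matters more if the true NBSS effect is below 11.8 or if retention is poor.

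**Conclusion.** The concern holds as a recommended improvement. The only between-group test the plan names for these outcomes uses neither the outcome's baseline as a covariate nor the randomisation stratum, and the mixed model leaves the role of baseline unspecified.

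If ρ lies between 0.3 and 0.9 and the SDs are equal, baseline adjustment removes 35% down to 5% of the variance. For NBSS at the planned effect this adds about 1 to 6 percentage points of power at 21–27 per arm. At an assumed 8 points it adds about 2 to 18. The I-QOL gain is small at either SD. All NBSS figures rest on reading 11 as the SD of change.

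The variance saving should not be read as a case for a smaller trial. Aim 1.1, a comparison of proportions, sets the sample size and is untouched by this point. The benefit is narrower intervals and less sensitivity to chance imbalance.

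**What to change.** In section 11.2, replace the change-score sentence with wording to this effect:

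- **I-QOL and anticholinergic survey:** compare week-12 scores between arms by ANCOVA, with the baseline score and the complete/incomplete SCI stratum as covariates.
- **NBSS:** analyse weeks 4, 8 and 12 in a repeated-measures mixed model with arm, visit, arm-by-visit, stratum and baseline NBSS, and report the week-12 contrast between arms. State whether baseline NBSS enters as a covariate or as a response with a common mean in both arms.
- **Wilcoxon test on change:** this can stay as a sensitivity analysis.

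State also which analysis is the main one for each outcome. The cost is SAP wording and one or two degrees of freedom. No extra data, visits or participants are needed.
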